2.2 INNOVATION

This project will be the first to establish if the anatomical links between ipRGCs and the amygdala translate into clinically meaningful changes in amygdala reactivity using morning light treatment. Amygdala hyperactivity has been associated with many different types of pathology that result from trauma exposure (i.e., PTSD, depression, anxiety) [23]; thus, we expect that if morning light treatment has a meaningful therapeutic effect on amygdala reactivity, it will have a broad impact on traumatic stress symptoms, potentially leading to a shift in clinical practice. The use of a wearable light device, the Re-Timer, which is user-friendly and enables the optimization of the therapeutic light wavelength, adds to the innovation by facilitating successful translation into future studies and practice.

3 RISK/BENEFIT ASSESSMENT

Overall, this study poses no more than minimal risk to the participant. The known risks fall into the following categories: risks associated with the research assessments, risk associated with the

intervention, risks associated with worsening mental or emotional state, and risk associated with breaches of privacy and confidentiality.

3.1 KNOWN POTENTIAL RISKS

3.1.1 Clinical assessments

The diagnostic and clinical interviews (SCID, HAM-D, etc.) and questionnaires are time consuming, and probe potentially sensitive topics like trauma history and suicidal ideation, etc. Some individuals might feel temporary distress at having to answer questions about their personal history. The instruments used in this study are well-tested and not known to cause persistent problems or distress; however, individuals are instructed that they can refuse to answer any question with which they are uncomfortable.

3.1.2 Worsening mental or emotional state

Some participants may show a worsening of psychological symptoms or suicidality during the course of the study period, regardless of assigned treatment arm. Among traumatized individuals, it is common for symptoms of emotional distress, including depression, hopelessness, and suicidal ideation to wax and wane. Thus, this risk is inherent in the population. We do not believe these risks are increased as a function of being enrolled in this study; if anything, we expect these symptoms to decrease as a function of being in the study. Participants will complete measures of anxiety, depression and suicidal ideation throughout the study, and be monitored by study staff and investigators for clinically significant changes.

3.1.3 fMRI

The potential risks such of undergoing a functional MRI are typically rare, and generally not considered dangerous or life threatening. They include:

- Discomfort or anxiety from being in the confined space of the MRI scanner
- The experience of peripheral nerve stimulation secondary (PNS) to fast imaging sequences, such
 as those employed in this study. PNS is often described as a light touching sensation on the skin
 surface and may cause mild discomfort, but is not harmful to the participant
- Hearing damage due to loud noises produced by the scanner
- Discovery of a previously unknown minor or significant lesion in the brain (e.g. a tumor) that might require additional follow-up
- Injury from objects accelerated by the strong magnetic field of the magnet, striking the
 participant; or metallic substances on the skin or foreign bodies implanted deliberately or
 accidentally in the participant that acquire kinetic or thermal energy from the magnetic or
 radiofrequency emissions of the MRI, causing tissue injury to the participant
- Temporary, slight dizziness or light-headedness when they come out of the scanner

The University of Michigan's fMRI Lab has well-established protocols for assessing and reducing risk, and addressing any arising complications. Participants in this study are screened multiple times for contraindications to MRI by the study staff and the fMRI Lab technicians. Women of childbearing potential are asked to complete a urine pregnancy test as part of standard fMRI Lab operating procedures. Once in the scanner, participants are provided with custom pads and pillows and ear plugs

to make the scanning process more comfortable. The machine is operated in accordance with FDA guidelines so the risk of PNS is low. Participants can communicate with study and fMRI lab staff via an intercom, and they can stop the testing at any time.

3.1.3.1 fMRI and pregnancy

According to the NIMH Council Workgroup on MRI Research and Practices (September, 2005), "there is no known risk of MR brain scanning of a pregnant woman to the developing fetus for scanning at 4T or less, and no known mechanism of potential risks under normal operating procedures." Nevertheless, participants should be warned about potential risks not yet discovered.

3.1.3.2 fMRI and incidental findings

During the formal consent process, all participants will be informed about the potential risks of discovering an incidental finding or abnormality on their MRI scan. If an abnormality is found in a participant's MRI scan, [name] (Co-I) will contact the participant and refer the participant for medical follow-up for the problem if the participant requests, including a referral to a primary care physician. If the participant has a primary care physician, [name] will contact the participant's doctor, at the request and with permission from the participant, to inform him/her of the finding on the MRI scan and to help him/her get the participant appropriate follow-up. The decision as to whether to proceed with further examination and/or treatment lies solely with the participant and his/her primary care physician.

3.1.3.3 Emotional Face Assessment Task (EFAT) & Emotional Regulation Task (ERT)

There is little risk associated with completing either the EFAT or ERT. Though unlikely, some individuals might report mild subjective anxiety. Co-investigator, [name] (licensed clinical psychologist) will be available during the task and MRI in the event of a more severe response such as anxiety/panic attack or distressing levels of anxiety. Participants will have an opportunity to preview examples of the images prior to getting into the scanner. If the study team has any doubts about relief of anxiety/distress, [name] will conduct follow-up telephone calls 1-3 days after the fMRI session to confirm the transient nature of the participant's reaction.

3.1.4 Morning Light Treatment

Reported side effects of morning light treatment are typically mild and short-lived [45, 46], and are rarely cause for discontinuation of treatment. Most commonly reported are headache, eyestrain, nausea and agitation. [45]

Some participants might experience jet lag type symptoms (e.g. transient sleepiness, fatigue and headache) like those seen when crossing 1 or 2 time zones because of circadian phase shifts secondary to morning light treatment. These symptoms are short-lived and are akin to what one might feel on a Monday morning after a late weekend.

A rare but serious side effect is mania in bipolar patients who overexpose themselves to the light [45, 46], but bipolar depressives are excluded from this study and all participants will be provided with strict instructions to limit their light treatment to 15 minutes, 30 minutes or 1 hour/day. Note that mania in response to morning light treatment is so rare that light treatment has even been clinically tested in bipolar patients and found to be safe [96].

The light treatment device used in this study, the Re-Timer is commercially-available, and meets all international ultraviolet and blue light hazard safety standards. The emitted light, while brighter than

most indoor light, is much dimmer than sunlight on a bright day; and the device has an auto-off feature after 1 hour of use.

3.1.5 Break of privacy or confidentiality

The collection of study data poses a potential risk of loss of confidentiality around sensitive information such as psychiatric status, history of substance abuse, etc. Participants will be informed in the consent document that confidentiality will be limited in cases where the participant reveals intentions to harm themselves or others, and the investigator feels that the proper authorities may need to be notified in order to prevent the occurrence of harm to the participant, or others. Interviews will be conducted by experienced mental health workers who will maintain confidentiality, and all data from interviews and questionnaires will be coded so as to conceal the identity of the participant.

Likewise, research data will be labeled with study codes rather than personal identifiers (e.g name, date of birth, MRN, etc.). Identifiers and PHI are maintained in a HIPAA-compliant database, and documents are stored in a locked file cabinet. Access to both electronic and physical data is restricted based on job responsibility.

3.1.5.1 Video Recording

The clinician-administered assessments will be videotaped. The recording equipment will be trained on both the clinician and the participant, so participants may be identified by their face and voice. Recordings are considered part of the research record and will be afforded the same level confidentiality. The recordings are not transcribed, but rather reviewed for training purposes and to assess clinician compliance with the administration guidelines. The video files will be stored in the study database on Michigan Medicine servers and will be available only to authorized study staff.

3.1.6 Unknown Risks

As with any research study, there might be risks that are unknown to the study team. The research and safety assessments, including both systematic and ad hoc monitoring, should contribute to capture of most adverse events and allow for the documentation of any heretofore unknown risks.

3.2 Known Potential Benefits

Participants may experience an improvement in their traumatic stress symptoms during the study either through the act of sharing information about their trauma or through the treatment itself, or even by their mere involvement with the study.

The potential benefit to others is that the study may advance our understanding of how morning light therapy may lead to therapeutic benefit for individuals affected by traumatic stress.

3.3 Assessment of Potential Risks & Benefits

Given that the potential risks associated with participating are minor and the potential benefits are considerable, it is believed that the risks are greatly outweighed by the benefits.

4 OBJECTIVES & ENDPOINTS

This study is a part of a larger proposal under the NIH R61/R33 mechanism which requires specific Go-No Go Criteria to transition between the two phases of the proposal. This protocol is specific to the R61 Phase. The specific aim and **objective for this phase** (i.e. study) is to **establish a significant dose response relationship between duration of morning light pulse and reduction in amygdala reactivity** from baseline to week 2 and/or week 4.

The **endpoint is whole-brain oxygen-level-dependent (BOLD) fMRI signal** using a priori regions of interest **specific to the bilateral amygdala**.

5 STUDY DESIGN

5.1 OVERALL DESIGN

- Single-blinded randomized controlled mechanistic trial
- Parallel groups
- 3 study arms based on light treatment duration: 15-minutes, 30-minutes or 60-minutes/day
- 4-weeks of morning bright light treatment delivered via Re-Timer device

This is a 5-week study (1-week of baseline and 4-weeks of intervention) that includes a screening visit plus 6 additional study visits to evaluate outcomes and monitor progress. Potential participants are prescreened for major exclusion criteria using a combination of online and telephone surveys. On Day 0 (Visit 1) individuals are consented and eligibility confirmed using several self-report questionnaires. Final eligibility is confirmed after the clinician interviews on visit 2 do not reveal any exclusionary psychiatric conditions (see below).

Participants return to the lab for study visit 2 for a battery of psychological assessments to characterize the sample, and to begin the week-long baseline period (see Section 1.3 - Schedule of Activities). At this visit, participants are provided with their study materials (Actiwatch Spectrum, daily log, instructions to sleep according to a normal schedule, etc.). To minimize burden participant burden and to accommodate calendar challenges (e.g. time change), the activities for this visit may be split across 2 days such that the psychological assessments are done on one day and the distribution and training of study materials occur on a second day within 1 months' time.

On Day 8 (Visit 3) participants return to the lab for randomization and baseline outcome assessments. Morning light treatment begins on the morning of Day 9. Thereafter, participants come to the research lab weekly to assess adherence to the study procedures and intervention, and monitor for side effects. Outcome assessments occur on Day 8, Day 22 (week 2 of intervention) and Day 36 (week 4 of intervention). The exact day number of study visits and activities can vary by up to a week; and we will try to schedule study visits for the same time of day. While the plan is to schedule the fMRI for the same day as the psychological assessments, we do allow for a 7-day window in cases where same-day scheduling is not possible.

Data collection is expected to last approximately 19 months with plans to enroll approximately 3 participants a month with possible exceptions for lower enrollment in November and March when offset and onset of daylight savings time can confound circadian rhythms and normal sleep habits.

6 Study Population

We plan to enroll 66 individuals with a recent history of DSM-5 Criterion A trauma and reported comorbid mood and arousal symptoms (as measured by the DASS questionnaire). These criteria are designed to include a wide variety of people with traumatic stress to maximize generalizability while ensuring that treatment and outcomes measures are not significantly affected by potential confounding variables. Additionally, we believe that this approach will lead to a transdiagnostic sample that shares the common feature of amygdala reactivity [11-14]. Diagnostic information will be collected via the Structured Clinician Interview for DSM Disorders (SCID-5-RV) [57] during Visit 2.

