1.3 SCHEDULE OF ACTIVITIES

Study Phase	Screening & Baseline 5																					I	nterv	entio	n												
Day Number 1							6	10	11	12	13	14	15	16	17	18	19	20	21	22	23	24	25	26	27	28	29	30	31	32	33	34	35	36			
Visit Number	٧1	v2 ⁶							٧3							٧4							٧5							9^							٧٧
Informed consent	Х																																				
Eligibility Confirmation	Х	х																																			
Vision Testing	Х																																				
Psychological assessment		Х																																			
Accelerometry		Χ	Χ	Χ	Х	Х	Х	Х	Х	Χ	Χ	Х	Х	Χ	Х	Х	Х	Х	Χ	Χ	Χ	Х	Х	Χ	Χ	Χ	Χ	Χ	Х	Х	Χ	Χ	Χ	Χ	Χ	Х	Χ
PSQI									Х														Х														Χ
Daily log ²		Х	Х	Х	Х	Х	Х	Х	Х	Χ	Х	Х	Х	Х	Х	Х	Х	Х	Х	Χ	Χ	Х	Х	Х	Χ	Χ	Χ	Χ	Х	Х	Χ	Χ	Χ	Х	Х	Х	Χ
Urine screen ³	Х	х							Х														Х														Χ
Breathalyzer	Х	Х							Х							Х							Х							Х							Χ
Clinician-administered assessments									х														Х														Х
Self-report questionnaires									Х							X ⁷							Х							X ⁷							Х
fMRI ⁴									Х																												Χ
Randomization									Х																												
Treatment expectation									Х																												
Light therapy										Χ	Х	Х	Х	Х	Х	Х	Х	Х	Х	Х	Х	Х	Х	Х	Х	Χ	Х	Χ	Х	Х	Χ	Χ	Х	Х	Х	Х	Х
Treatment fidelity – daily contact										Х	Х	х	х	Х	х	Х	х	х	Х	Х	Х	Х	Х	Х	Х	Х	Х	Х	х	х	Х	Х	Х	Х	Х	Х	Х
Treatment fidelity – data download & feedback																х							х							х							Х
AE Assessment (SAFTEE/CSSRS)	х	х							Х							Х							Х							Х							Х
Treatment satisfaction																																					Χ

^{1 –} Exact day number can vary by up to one week; 2 – Daily log will capture information about sleep time, treatment time, medication use, etc.; 3 – Urine drug screen administered via dipstick by study team at baseline and urine pregnancy screen to ensure drug free participants; 4 – fMRI must occur within 7 days of clinician-administered assessments; 5 – Final screening and eligibility confirmation occur on day 0/v1 and the start of the weeklong baseline period begins at v2; 6 – Visit 2 activities may be split across 2 days separated by no more than 1 month; 7 – Only the PCL-5 and DASS will be administered at these visits

2 Introduction

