6.5 Participant Incentives

Participants are eligible for up to \$1210.00 in incentive payments. The payment plan was designed to partially compensate individuals for the burden of the study visits and associated travel costs, as well as promote study completion by including a bonus for finishing the protocol. Participants will be paid as the study progresses for those parts of the study completed.

- Visit 1 \$20 for screening visit eligibility confirmation and consent
- Visit 2 Receive study materials, no incentive
- Visit 3 \$225
 - \$75 for completing the baseline week of actigraphy and activity/sleep logs
 - \$150 for completing the clinical assessments and fMRI
- Visit 4 \$75 for completing previous week of actigraphy and activity/sleep logs
- Visit 5 \$175
 - \$75 for completing previous week of actigraphy and activity/sleep logs
 - \$100 for completing clinical assessments
- Visit 6 \$75 for completing previous week of actigraphy and activity/sleep logs
- Visit 7 \$400
 - \$75 for completing previous week of actigraphy and activity/sleep logs
 - \$150 for completing clinical assessments and fMRI
 - \$175 bonus for completing the study
- Travel stipend \$80 \$240 for Visit 1-7 (e.g. up to 8 visits to the research clinic including coming to the clinic twice for activities associated with Visit 2)
 - The travel stipend will be \$10 \$30 per study visit to account for the varying distance which different participants must travel to the lab. The travel stipend will always be at least \$10, increasing by approximately \$1 per mile traveled, up to a maximum of \$30 for 30 miles or more. Mileage will be rounded up to the nearest whole number to determine the dollar amount given, e.g., 10.4 miles would amount to a travel allowance of \$11.
 - Participants will be asked to verify from which location they will be traveling to lab visits during their phone screen and reconfirm this at Lab Visit 1, which will determine their stipend for Visits 1-7.

o If the fMRI occurs on a different day from the research clinic visit, the travel stipend is only provided for the visit to the clinic (e.g. Rachel Upjohn Building).

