7.2 Administration & Dosing

- Self-administered in own home
- First thing upon waking (or up to 1 hour earlier to accommodate morning commitments like work or childcare)
- Light intensity is about 500 lux
- Duration is pre-set for either 15, 30 or 60 minutes/day depending on study arm
- Daily administration for 4 consecutive weeks (starting the morning after Visit 3)

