9.7 FMRI

Amygdala reactivity will be measured using fMRI and change in BOLD signal measures across the study period. Images will be acquired using an Echo-Planar Imaging sequence (TR=800 ms, FOV=23, slice=2.4mm, 96x96 matrix) to measure brain function at rest and during the EFAT task, optimized to reduce susceptibility artifact. fMRIs (initially at visits 3, 5 and 7 but later changed to only visits 3 and 7) will be scheduled at the North Campus facility and must occur within 7 days of the clinician-administered and self-reported assessments of trauma stress and mood (see Section 9.3)

9.7.1 fMRI Practice

As part of the screening process, individuals will be able to lie in the mock scanner located at the Rachel Upjohn Building. This scanner is built to size, and includes simulating scanner noise from speakers so people can hear the noises associated with scanning.

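### The fMRI window is not tied to light: a baseline scan may follow up to 7 light sessions, and the final scan may fall anywhere from Day 29 to Day 43

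*Combined protocol and SAP*

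**What the plan says.** Two windows apply to the scans.

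- **Visit days.** Section 5.1: "The exact day number of study visits and activities can vary by up to a week". Footnote 1 of the Schedule of Activities (section 1.3) agrees: "Exact day number can vary by up to one week".
- **fMRI.** Section 5.1 plans the scan for the day of the psychological assessments, but "we do allow for a 7-day window in cases where same-day scheduling is not possible". Footnote 4 of section 1.3 reads "fMRI must occur within 7 days of clinician-administered assessments", and section 9.7 repeats the limit. None of these says before or after.

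Scans on another day are provided for: section 6.5 has a stipend rule that begins "If the fMRI occurs on a different day from the research clinic visit".

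Light has its own anchor. Section 7.2 gives "Daily administration for 4 consecutive weeks (starting the morning after Visit 3"), and section 5.1 puts the first session on Day 9. The light row of the Schedule of Activities runs through Visit 7.

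Section 9.7 says scans were "initially at visits 3, 5 and 7 but later changed to only visits 3 and 7". Section 4 and section 11.1 define the objective as a dose-related reduction from baseline to week 2 and/or week 4. Section 11.1.2 sets the Go/No-go threshold at Cohen's d of 0.5 or more in one of the three durations.

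**The concern.** Nothing in the text connects either window to the light course. No rule puts the baseline scan ahead of the first session, ties the final scan to the last session, or says whether the two windows may be added.

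The baseline scan is the sharper problem. Randomisation takes place at Visit 3, so a scan some days later may already reflect the assigned dose. If the trial's hypothesis is right, such a scan reads low, and lowest in the 60-minute arm. That shrinks the change within each arm. It also shrinks the dose-by-time interaction, which section 11.2 uses as the test and for which its own example assumes no group difference at baseline.

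The final scan matters because, for participants scanned only at Visits 3 and 7, it is the only follow-up measurement. Some earlier participants may also have a week-2 scan. If the final scan is taken at varying points of the course, or after light has stopped, the meaning of week 4 is blurred and noise is added.

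**Working it through.** **Inputs.** Visit 3 is Day 8, first light is Day 9 and Visit 7 is Day 36 (section 5.1). Light lasts 4 consecutive weeks (section 7.2). Both windows are 7 days (sections 1.3 and 5.1).

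**1. The planned course.** Days 9 to 36 give 36 − 9 + 1 = 28 sessions. This matches the stated 4 weeks and puts the last session on the planned day of Visit 7.

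**2. Baseline scan.** The latest day is 8 + 7 = Day 15. Sessions by then: 15 − 9 + 1 = 7 if that morning's session comes first, or 6 if it does not. Seven of 28 is 25% of the course, leaving 28 − 7 = 21 sessions between the scans. A scan up to 7 days before Visit 3 does no harm.

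**3. Final scan, using one window only.**

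| Scan day | Sessions before scan | Days without light |
|---|---|---|
| 29 (36 − 7) | 29 − 9 + 1 = 21 (75%) | 0 |
| 36 (planned) | 28 (100%) | 0 |
| 43 (36 + 7), light stops after 4 weeks | 28 (100%) | 43 − 36 = 7 |
| 43, light continues to Visit 7 or the scan | 43 − 9 + 1 = 35 (125%) | 0 |

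If both windows were used in the same direction, the scan could fall on Day 22 (14 sessions) or on Day 50 (14 days without light, if light stops). The text does not exclude this, but the point does not rest on it. If the calendar slides as a block at or before Visit 3, the final scan still follows 28 sessions.

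**4. Two-sided illustration.** Assume that the effect builds evenly over 28 sessions, that the standard deviation is unchanged, and that every shift is a full week. Let b be the share of participants with a late baseline scan, e the share with an early final scan, and l the share with a late final scan with light continued. Then

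measured d = true d × (1 − 0.25b − 0.25e + 0.25l).

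For a true d of 0.50 and an assumed share of 25%:

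- late baseline only, or early final only: 0.50 × 0.9375 = 0.469
- late final only, light continued: 0.50 × 1.0625 = 0.531
- equal shares of early and late final scans: 0.50

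A late final scan after light has stopped loses nothing here unless the effect decays. For assumed shares of 10%, 25% and 50% in one direction, the shift is 0.0125, 0.031 or 0.0625 in d.

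**5. Comparison with sampling error.** The protocol does not define d. Take it as a within-arm standardised change, with equal allocation and complete data: 66 / 3 = 22 per arm. Then SE ≈ √(1/n + d²/(2n)) = √(1/22 + 0.25/44) = √0.0511 ≈ 0.23. The shifts in step 4 are about 6%, 14% and 28% of one SE.

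**The case against.** The strongest reply is that the intent is clear. Section 5.1 calls the Visit 3 measurements baseline outcomes and then starts light the next day. The schedule places the scan at Visit 3, and section 6.3.1 treats Visit 3 as coming before light. The plan is same-day scanning, and the window can be met by scanning earlier. All of this is true of the intent. But the window has no direction and light starts regardless of the scan, so the written rule still allows a scan after first light.

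For the final scan, the reply is that visits and activities may move together, and that the light row through Visit 7 suggests light continues. This stands in part: 7 days without light is only one reading, and 35 sessions is another. Neither is the planned 28.

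The model has time as a predictor (section 11.1). Continuous time based on actual scan dates could absorb some of the spread in the final scan. The plan does not say that actual dates are used, and no coding of time restores an untreated baseline.

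Even build-up is also an assumption. Section 2.1.2 cites antidepressant effects that were significant by 2 weeks. A faster build-up would make an early final scan cost less and a late baseline scan cost more.

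A reader might also infer that safety checks can lie 14 days apart, because the visit window equals the visit interval. The documents do not support that as a finding. Visits are described as weekly in sections 5.1, 6.4.7, 7.3 and 9.10.1, and the payments in section 6.5 are "for completing previous week of actigraphy and activity/sleep logs". Section 10 makes the Data and Safety Monitoring Plan the definitive source, and that plan is not among the documents reviewed.

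**Conclusion.** The concern holds as a gap in the scan-timing rules, of minor to moderate weight. As written, the baseline scan can follow up to 7 of 28 sessions of the randomised dose. The final scan can fall on Days 29 to 43, after 21 sessions, after 28 sessions plus up to 7 days off, or after up to 35 sessions. If light works, the baseline fault biases towards zero. The final-scan fault mainly adds noise and can go either way.

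The size is unknown because use of the windows is unknown. It is probably small relative to sampling error, given the assumptions in steps 4 and 5. A reader might infer that the windows would make the trial miss its 0.5 threshold. The documents do not support that: it would need frequent full-week shifts in one direction, and the protocol plans same-day scans.

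**What to change.** 1. **Baseline.** Require the baseline scan before the first session: light starts the morning after Visit 3 or after the baseline scan, whichever is later.
2. **Final scan.** Time it to the end of the light course in a narrower window, for example Day 36 ± 3 (the width is a judgement). If the scan is delayed, continue daily light to the morning of the scan. With light on schedule, that gives 33 − 9 + 1 = 25 to 39 − 9 + 1 = 31 sessions. State that the visit and fMRI windows do not add. Because the last scheduled Re-Timer download is at Visit 7, participants scanned later should keep the glasses and log until the scan.
3. **Analysis.** From the downloads and logs already collected, derive sessions completed and days since last light at each scan. Repeat the primary model as a sensitivity analysis, excluding baseline scans after first light and final scans outside the window. Keep it secondary, because sessions completed is a post-randomisation variable. This step can be done even if scanning has finished.

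The cost is protocol wording, two derived variables and one extra analysis. The downside is slightly less scheduling freedom, and a later start of light or a few extra sessions for some participants.
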